6.2.4. Post-Treatment Evaluation

After treatment termination the patient will be seen at an outpatient clinic every month for two additional visits. Physical and neurological examination, blood tests (CBC and Chemistry panel) will be performed during these visits. Patient mortality and adverse events will be documented on the case report forms. After the two post treatment monthly follow up visits, patients will not be required to return to the clinic for follow-up but will be followed monthly until death by telephone to monitor their status.

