Investigational Product/ Background	NOVOTTF-200A will be administered with a monthly adherence rate goal of $\geq 75\%$ (≥ 18 hours daily) of therapy over a 4-week cycle in subjects with recurrent G3 MG who have not previously been treated with any anti-

Therapy/ Route/ Regimen	angiogenic agent including BEV.
Procedures	
Study visits and procedures will be performed as outlined in Table 1.
 
The study will consist of Screening, Treatment and Follow-Up periods.
 
Screening:
 
The screening period may not exceed a 28-day window prior to start of study treatment (Cycle 1, Day 1). Assessments will include medical history, cancer history including previous treatments, physical examination and tumor assessments. Tumor assessment must have a baseline MRI scan with contrast within 14 (+3) days prior to first treatment with investigational product. Vital signs measurement and laboratory tests are to be conducted within 7 days prior to Cycle 1, Day 1.
 
Treatment:
 
Subjects may continue on study treatment until disease progression, unacceptable toxicity, withdrawal of consent or termination of the study. Assessment will include MRI scans at the end of every even numbered cycle (± 7 days) using RANO (2010) criteria for assessment. Subjects who discontinue study therapy for reasons other than disease progression whenever possible will continue tumor assessment as per protocol schedule until progression.
 
Safety Follow-Up (End-of-Treatment Visit):
 
Subject will be followed for safety for 28 (+3) days after discontinuation of trial therapy (NOVOTTF-200A)
 
Survival Follow-Up:
 
All subjects will be followed in the long-term survival follow-up period for as long as they are alive. Long-term follow-up will occur every 3 months (± 7 days) after the 28-day post-treatment discontinuation visit. Telephone contact will be sufficient to document survival status. During the follow-up period, the following information will be collected: survival, and subsequent anti-malignant glioma regimens (regimen, start and end date and treatment outcome).

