3.3. Study Duration

Subjects may continue on study treatment until disease progression, unacceptable toxicity, withdrawal of consent, or termination of the study. Once discontinued from the study treatment, subjects will enter a long-term follow-up period for documentation of survival and the start of first new anti-glioma therapy and its outcome. Long-term follow-up will occur every 3 months (± 7 days) after the 28-day post-treatment discontinuation visit.

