8. STATISTICAL CONSIDERATIONS

Efficacy: Tumor response, including PD, progression-free survival (PFS), and overall survival (OS) will be assessed. Tumor response will be assessed by the Investigators using RANO 2010 criteria. The overall confirmed response rate will be presented. Primary outcome variable will be 6-month PFS. In addition, response rate will also be measured taking into account partial response and complete response.

Primary Objective: The primary objective is to estimate the proportion of participants showing no evidence of disease progression six months after initiating treatment with the device (PFS₆). We will compute interval estimates of this proportion. This information will inform decisions about further research on this device (or similar approaches). We will also document issues of intolerability and all adverse events.

Primary Efficacy Endpoint: The primary efficacy endpoint is disease status six months from initiation of treatment with the device. Assessment is per RANO (2010) criteria. The primary efficacy measure is the 90-percent interval estimate of PFS₆.

Primary Adverse Event Measures. Adverse events will be recorded, including time-on-treatment and an assessment of likely relation to device use. Reasons for discontinuing use of the device will be recorded to the fullest extent possible.

Analysis Data Sets for Efficacy: The primary efficacy analyses will be conducted on the intent-to-treat data set (ITT), defined as including all participants receiving at least one exposure to the active device. Supplemental analyses will be performed on the per-protocol data set (PP), defined as including only those participants meeting the minimum prescription for device use (≥ 18 hours daily over a four-week cycle).

Variables to be Collected. In addition to adverse events, reasons for discontinuation, disease trajectory, mutation status (viz., ATRX, TERT, IDH1, MGMT), Karnofsky performance status, and psychometrics (viz., FACT-Br, FACT-Cog), information on patient demographics, host factors, and co-morbidities will be collected for use in exploratory analyses. Survival will be tracked until death or the end of the project. Information on further anti-glioma treatments received after patients are off of this study will be sought.

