11. CRITERIA FOR REMOVAL FROM STUDY

Any serious adverse event deemed life threatening by the treating physician that is definitely related to the study device will be cause for immediate cessation of treatment for the patient. Patient follow up will continue after the event.

- The investigator may remove a patient from the study in case of not complying with study protocol.
- Patients will be able to withdraw from the study at their own request .

The following events are considered sufficient reasons for discontinuing a subject from the investigational product and/or from the study:

- Protocol Violation
- Non-Compliance
- Adverse Event
- Subject Developed a DLT
- Subject Decision
- Withdrew Consent
- Investigator Decision
- Disease Progression
- Pregnancy
- Death
- Other

The reason for discontinuation should be recorded in the CRF and in the source documents.

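### The synopsis continues scans after early device stop but the body does not, and no rule says how an exposed participant with unknown six-month status counts in the primary proportion

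*Combined protocol and SAP*

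**What the plan says.** **Endpoint and analysis set.** Section 8 states: "The primary efficacy endpoint is disease status six months from initiation of treatment with the device". Assessment is by RANO 2010. The proportion counts participants with "no evidence of disease progression six months after initiating treatment with the device". The primary set, labelled ITT, is "defined as including all participants receiving at least one exposure to the active device". Section 8.1 reports it as an exact 90% interval.

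**Scanning after early stop, synopsis.** Under Procedures (Treatment): "Subjects who discontinue study therapy for reasons other than disease progression whenever possible will continue tumor assessment as per protocol schedule until progression". The synopsis entry on length of participation says the same in substance. Footnote 12 of the schedule of assessments adds a scan at the End-of-Treatment Visit if none was done in the preceding four weeks.

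**Scanning after early stop, body.** Section 3.3: "Once discontinued from the study treatment, subjects will enter a long-term follow-up period for documentation of survival", together with new therapy and its outcome. Section 4 lists survival, later regimens and their outcomes. Section 6.2.4 provides two monthly visits with examination and blood tests, then telephone contact: "After the two post treatment monthly follow up visits, patients will not be required to return to the clinic for follow-up". The post-study column of the schedule of assessments has no tumor measurement.

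**Removal.** Section 11: "The investigator may remove a patient from the study in case of not complying with study protocol".

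**Numbers.** Up to 36 enrolled; 26 evaluable needed (synopsis, Sections 3.1 and 5.1); precision computed for 34 (Section 8.1). Evaluable is not defined.

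**The concern.** The primary proportion needs a six-month disease status for every exposed participant. A site that follows the body rather than the synopsis may stop scanning someone who left the device early without progression, and a participant removed under Section 11 may have no further assessment.

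The plan then supports opposite counts. Taken literally, the Section 8 wording makes an unscanned participant a success, because nothing shows progression. Taken through the evaluable number, the same participant drops out of the denominator.

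Section 3.1 lists device-related serious events and clinical deterioration among the reasons for stopping, so missing status may be related to outcome. There is no control arm in which the same handling would operate. The futility check is exposed too: it is met only if none of the first nine is progression-free, so one unscanned participant read as a success would prevent it. If the rule is chosen after open-label data have been seen, the main result depends on that choice.

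**Working it through.** **1. The passages side by side, for a participant who stops the device at month 2 without progression**

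- Synopsis: scans continue on schedule until progression, where feasible.
- Footnote 12: at most one scan around the End-of-Treatment Visit, which can fall well before month six.
- Section 3.1: two-monthly MRI is described for the period on treatment.
- Sections 3.3, 4 and 6.2.4: no scan listed after the End-of-Treatment Visit. Section 6.2.2 labels the same two months as coming after progression, which overlooks this participant.
- Section 7.2: starting another anti-tumor drug counts as progression. That settles status for some early stoppers only.

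Six-month status may be obtained under the synopsis and may be missing under the body.

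**2. The plan's own precision figures**

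For x successes in n, the exact 90% limits are: lower = 5th percentile of Beta(x, n−x+1); upper = 95th percentile of Beta(x+1, n−x). Summing binomial probabilities over all x whose half-width is within the target, at n = 34:

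| True rate | within 13 points | within 15 | within 16 |
|---|---|---|---|
| 25% | 0.357 | 0.988 | 1.000 |
| 35% | 0.053 | 0.830 | 1.000 |
| 45% | 0.003 | 0.468 | 1.000 |

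Section 8.1 prints 0.36/0.99/0.99, 0.05/0.83/0.99 and 0.00/0.47/0.99. The table reproduces, apart from 0.99 printed where the value is 1.00. The method is therefore the exact interval at n = 34.

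**3. Effect of the unstated counting rule**

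Inputs: N = 36 exposed (Section 8.1); k with unknown status; s documented successes among the N−k known. I assume about 45% progression-free among known cases, one of the rates in the plan's table.

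- k = 2, from 36 − 34, the only loss Section 8.1 implies: s = 15 (0.45 × 34 = 15.3).
- k = 6, assumed: s = 14 (0.45 × 30 = 13.5).
- k = 10, assumed extreme from 36 − 26: s = 12 (0.45 × 26 = 11.7).

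Estimates: failures s/N; dropped s/(N−k); successes (s+k)/N.

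| k | Failures | Dropped | Successes |
|---|---|---|---|
| 2 | 15/36 = 41.7% (27.7–56.7) | 15/34 = 44.1% (29.5–59.5) | 17/36 = 47.2% (32.8–62.0) |
| 6 | 14/36 = 38.9% (25.3–54.0) | 14/30 = 46.7% (30.8–63.0) | 20/36 = 55.6% (40.6–69.8) |
| 10 | 12/36 = 33.3% (20.5–48.3) | 12/26 = 46.2% (29.2–63.8) | 22/36 = 61.1% (46.0–74.7) |

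The failures-to-successes spread is k/36: 5.6, 16.7 and 27.8 points. Dropping exceeds counting as failures by about 2.5, 7.8 and 12.8 points.

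**4. Precision if only 26 are analyzed**

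The calculation of step 2 at n = 26 gives a probability of a half-width within 16 points of 0.69, 0.26 and 0.05 at true rates of 25%, 35% and 45%, against 1.00 at n = 34. The meaning of evaluable therefore affects precision as well as the estimate.

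**The case against.** A reader might infer that early stoppers are not scanned at all and have no six-month status. The documents do not support that. The synopsis provides twice for continued assessment, footnote 12 can add an End-of-Treatment scan, and Section 3.1 makes progression, not device stop, the point after which MRI is no longer required. Sections 6.2.2 and 6.2.4 read as if written for patients who have already progressed, and they do not forbid scans. What stands is that status may be missing.

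A reader might also infer that the plan expects 10 unevaluable participants. It does not: 36 is a ceiling, 26 is a minimum, and the only loss Section 8.1 implies is 2. Ten is an extreme, and its 27.8-point spread should be set against the full planned interval width of 30 to 32 points (twice 15 to 16), not the half-width.

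Nor is upward bias established. Counting unknowns as successes biases upward. Dropping them does so only if they would have done worse than those observed, which no passage shows. Counting all of them as failures can bias downward.

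Other points are fair. An unassessed participant has no RANO status, so counting one as a success is a strained reading. Non-adherent but exposed participants remain in the ITT set by definition, and Section 11's list allows discontinuation from the device alone. Kaplan-Meier PFS is already planned. The trial estimates a proportion and has no primary hypothesis test. None of this supplies the missing rule or removes the conflict between synopsis and body.

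**Conclusion.** The point holds in this form: the documents conflict on scanning after early device stop, Section 11 permits removal without saying that outcome assessment continues, and no rule covers exposed participants whose six-month status is unknown.

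The size depends on how many there are. At the plan's implied loss of 2, the choice of rule moves the estimate by up to 5.6 points, which is modest. At 6 unknowns it moves by 16.7 points, about one planned half-width. These figures assume 36 exposed and about 45% progression-free among known cases; 6 and 10 unknowns are assumptions, not plan figures. The direction of bias cannot be stated until the rule is. Because this concerns the trial's main number and the remedy is wording, it should be settled before outcome data are examined.

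**What to change.** 1. **Sections 3.3, 4, 6.2.4 and the schedule of assessments.** Reconcile these with the synopsis so that, after early device stop for reasons other than progression, tumor assessment continues at least through the six-month assessment.
2. **Section 8.** Keep every exposed participant in the primary denominator. Count as progression-free only those alive with a RANO assessment, at or after the six-month assessment, showing no progression, and with no other anti-tumor medication (Section 7.2). Count unknown status as not progression-free. State the assessment window: with 28-day cycles and scans after even-numbered cycles, the nearest scans fall near day 168 (6 × 28) and day 224 (8 × 28). Report the already planned Kaplan-Meier PFS at six months as a sensitivity analysis. Define evaluable against 34 and 36, or delete it.
3. **Section 11.** State that outcome follow-up continues whatever the reason the device is stopped, unless consent is withdrawn. This leaves the rules on when the device is stopped untouched.

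The cost is a protocol amendment; the scans are already promised in the synopsis. The drawback is a somewhat conservative estimate if missing status is unrelated to outcome, which comparison with the Kaplan-Meier estimate would help to show.

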6.3. Method of Treatment Assignment

Single arm study. All the patients will receive NOVOTTF-200A treatment.

6.4. Packaging and Labeling

The label(s) for Investigational Product (IP) NOVOTTF-200A will include manufacturer name, address and telephone number, the protocol number, IP name, device identification/kit number, instructions, storage conditions, technician contact information, and required caution statements and/or regulatory statements as applicable. Additional information may be included on the label as applicable per local regulations.

6.5. Investigational Product Accountability and Disposal

Designee of the study team will review with the subject the process for Investigational Product return.

7. Concomitant Medications and Procedures

7.1. Permitted Concomitant Medications and Procedures

Concomitant medications to treat comorbid conditions and adverse events are permitted. Enzyme-inducing anti-epileptic drugs (EIAEDs) are allowed. Steroids are allowed and dosing is at the discretion of the investigator.

7.2. Prohibited Concomitant Medications and Procedures

Medications to treat the underlying malignancy are not permitted and their use constitutes progressive disease and subjects must discontinue study treatment. Investigational agents of any kind are not permitted.

7.3. Required Concomitant Medications and Procedures

There are no required concomitant medications or procedures.

8. STATISTICAL CONSIDERATIONS

Efficacy: Tumor response, including PD, progression-free survival (PFS), and overall survival (OS) will be assessed. Tumor response will be assessed by the Investigators using RANO 2010 criteria. The overall confirmed response rate will be presented. Primary outcome variable will be 6-month PFS. In addition, response rate will also be measured taking into account partial response and complete response.

Primary Objective: The primary objective is to estimate the proportion of participants showing no evidence of disease progression six months after initiating treatment with the device (PFS₆). We will compute interval estimates of this proportion. This information will inform decisions about further research on this device (or similar approaches). We will also document issues of intolerability and all adverse events.

Primary Efficacy Endpoint: The primary efficacy endpoint is disease status six months from initiation of treatment with the device. Assessment is per RANO (2010) criteria. The primary efficacy measure is the 90-percent interval estimate of PFS₆.

Primary Adverse Event Measures. Adverse events will be recorded, including time-on-treatment and an assessment of likely relation to device use. Reasons for discontinuing use of the device will be recorded to the fullest extent possible.

Analysis Data Sets for Efficacy: The primary efficacy analyses will be conducted on the intent-to-treat data set (ITT), defined as including all participants receiving at least one exposure to the active device. Supplemental analyses will be performed on the per-protocol data set (PP), defined as including only those participants meeting the minimum prescription for device use (≥ 18 hours daily over a four-week cycle).

Variables to be Collected. In addition to adverse events, reasons for discontinuation, disease trajectory, mutation status (viz., ATRX, TERT, IDH1, MGMT), Karnofsky performance status, and psychometrics (viz., FACT-Br, FACT-Cog), information on patient demographics, host factors, and co-morbidities will be collected for use in exploratory analyses. Survival will be tracked until death or the end of the project. Information on further anti-glioma treatments received after patients are off of this study will be sought.

Design: This is a single-center, single-arm, open-label, Phase-IIA clinical trial to estimate PFS₆ under the conditions of the trial and to gather information on safety and tolerability associated with the device in clinical use.

8.1. Sample Size: Justification of Sample Size: Data from 36 participants will yield a 90-percent interval estimate of PFS₆ with sufficient precision for our purposes. Table 1 shows the probability of observing a 90-percent confidence interval from 34 participants at various levels of the population proportion and confidence-interval half widths. The table is based on 34 rather than 36 participants, anticipating some loss of participants to the exigencies of research.

The table shows over 90-percent power to estimate PFS₆ to plus or minus 16 percent at all levels of the population proportion shown. The power to estimate PFS₆ to plus or minus 15

percent is adequate for the more extreme levels of population proportion, but perhaps not when the latter is near 50 percent.

Table 1. Probability of Observing a 90-Percent Binomial Confidence Interval Given 34 Subjects for the Indicated Underlying True Proportions and Interval Half Widths

Population Proportion	Interval Half-Width		
	13%	15%	16%
25%	0.36	0.99	0.99
35%	0.05	0.83	0.99
45%	0.00	0.47	0.99
55%	0.00	0.47	0.99
65%	0.05	0.83	0.99
75%	0.36	0.99	0.99

Rounded to nearest one hundredth, exact method, 2-sided, SAS Power and Sample Size v3.1

Futility Assessment. If none of the first nine participants is progression-free at six months from initial use of the device, then serious consideration will be given to stopping the project for futility. This criterion is adopted from the Simon, two-stage, optimal design (null-hypothesis rate of 5% v alternate- hypothesis rate of 25%). A formal decision to stop the trial will depend upon the clinical judgment of the medical director.

Intolerability Assessment. Intolerability and adverse events will be closely monitored by the treating physicians. A decision to stop the project for intolerability will be based on clinical judgment of the medical director.

Primary Analyses for Efficacy: The 90-percent interval estimate of PFS6 is the primary summary of efficacy in this project. Exact methods will be used.

Secondary Analyses for Efficacy: We will examine the data in many ways to inform decisions about further research, including plots, tables, and statistical tests, accounting for repeated measures where appropriate. Participants will be described by sex, age, and other host or clinical factors, using means, medians, and percentiles for continuous variables and counts and percentages for categorical variables. The FACT-Br and FACT-Cog will be scored in the standard way (Weitzner et al, 1995). Both progression-free and overall survival will be estimated by Kaplan-Meier methods, both overall and by strata of interest. Differences in survival between or among groups will be evaluated by the log-rank test. If the assumptions are reasonably met, then Cox proportional-hazards models will examine the effects on survival of covariates adjusting for other covariates. Ties in survival time will be broken by the subtracting a small, randomly generated amount from each tied observation (Borucka, 2014). Secondary analyses will be performed on both the ITT and PP data sets, as seems warranted. For secondary analyses, the probability values from statistical tests will be used as a guide to interpretation, which will also depend on clinical judgment. Therefore, we will not be concerned with overall, study-wise, type-1 error rates for the secondary analyses.

Analyses for Intolerability or Toxicity: We will examine the data to discover factors that may predict adverse reactions to the study treatment. We will proceed in the same way as outlined

above for secondary analyses for efficacy. As the goals of these analyses are to inform decisions about future research, no formal statistical hypothesis testing will be done, probabilities from statistical tests will augment clinical judgment in interpretation, and we will not regard overall, study-wise, error rates.

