Physical examination, height ²		X				
Targeted physical, weight, BSA, KPS ²		X	X	X	X	
Toxicity evaluation ³			X	X		
Vital signs (HR, temp, BP) ⁴		X	X	X	X	
ECG ⁵		X			X	
CBC, Diff, Platelets ⁶		X		X	X	
Serum Chemistry ⁷		X		X	X	
PT/PTT ⁸		X			X	
Urinalysis ⁹		X			X	
NovoTTF-200AoTTF-isis ¹⁰			X	X		
Pregnancy test ¹¹		X			X	
Tumor measurement ¹²	X (-14 to -1)			End of even numbered cycle		
Tumor gene signature profiling ¹³	X					
Quality of Life Questionnaires ¹⁴	X			End of even numbered		

1. Within 7 days of starting treatment except consent, demographics, medical history, concomitant medications, complete physical examination, radiographic/tumor assessments, and consent to acquire and test archival tumor tissue samples which can be obtained within 28 days prior to the start of treatment.
2. Height measured at baseline only. Physical Examination is a complete physical as per institutional guidelines (genitourinary examination not required unless there are related signs or symptoms) at baseline but thereafter as directed by signs and symptoms (focused physical examination). Karnofsky Performance Status (KPS) is according the Karnofsky scale (see Appendix A).
3. Toxicity evaluation is an assessment of reported and observed adverse events following the NOVOTTF-200A administrations compared to pre-treatment findings.
4. Vital Signs: (blood pressure, heart rate and temperature) Day 1 of every cycle. Vital signs are also collected as part of the physical examination.
5. ECG: to be done at the baseline and the end-of-treatment visit.
6. Hemoglobin (Hgb), hematocrit (Hct), red blood cell (RBC) count, white blood cell (WBC) count with differential and platelets as per standard of care.
7. Sodium, potassium, chloride, bicarbonate, calcium, magnesium, glucose, BUN, serum creatinine, uric acid, ALT, AST, alkaline phosphatase, total protein, albumin and total bilirubin as per standard of care.
8. Prothrombin time (PT) or International Normalized Ratio (INR) and partial thromboplastin time (PTT) may be performed if clinically indicated.
9. Urinalysis: to be done at the baseline and the end-of-treatment visit.
10. NOVOTTF-200A: therapy: To initiate on Day 1, Cycle 1 and be continued from Cycle 2 on with monthly adherence rate $\geq 75\%$ (≥ 18 hours daily) of therapy over each 4-week cycle in subjects until progression.

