A pilot study was performed on ten recurrent GBM patients treated with the NovoTTF- 200A device. All patients underwent surgery and radiotherapy for the primary tumor. Only 1 patient was chemotherapy naïve, the rest having received either temozolomide or other chemotherapeutic agents, as adjuvant treatment, prior to recurrence.

All patients were treated with multiple four-week treatment courses using continuous, 24-hour a day, 200 kHz, 0.7 V/cm TTFields. TTFields were applied through two sets of opposing insulated electrode arrays and alternated at a 1 second duty cycle between two perpendicular field directions through the tumor. Patients completed between 1 and 15 treatment courses leading to maximal treatment duration of 14.5 months. Overall, more than 70, 4 week treatment courses were completed (> 7 courses per patient on average).

The treatment was well tolerated with no treatment related serious adverse events seen in any of the patients. Patients received treatment on average about three quarters of the scheduled time. Considering the continuous nature of NovoTTF treatment (i.e., 24 hours a day for many months) this figure indicates that compliance with treatment was very high, with patients taking very few days off treatment and stopping only for short periods of time during treatment for personal needs.

Mild to moderate contact dermatitis appeared beneath the electrode gel in 8 of the 10 patients during treatment. In most cases this dermatitis appeared for the first time during the second treatment course. The skin reaction improved with use of topical corticosteroids. Regular relocation of the electrode arrays was necessary in order to allow for continuous treatment.

The median progression free survival (PFS) of the patients in this study exceeded historical controls (26.1 weeks versus 9 weeks, respectively). The PFS at 6 months (PFS6) was 50% compared to 15% in historical controls. Median overall survival was 62 weeks.

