3. OVERALL STUDY DESIGN

3.1. Study Design

This is a Phase 2, single arm study in subjects with AA who had progressive disease during first-line treatment or who are in first or second relapse and who have not previously received any bevacizumab (BEV) or other anti-angiogenic agent, including sorafenib, sunitinib, axitinib, pazopanib or cilengitide. Up to 36 subjects will be enrolled with 26 evaluable patients needed.

The determination of whether to stop treatment due to progression will be based on the investigator's evaluation of the patient's clinical condition. NovoTTF-200A treatment may be continued until disease progression, unacceptable toxicity, withdrawal of consent, or termination of the study. In the case of radiological progression, NOVOTTF-200A treatment will be stopped and a different treatment will be chosen instead by the investigator.

Patients will be recruited to the study by the principal investigator (PI) or one of the coinvestigators (CI) at UC Irvine. Patient accrual is expected to continue for 24-36 months.

NovoTTF-200A treatment will be given alone for this single arm study. At treatment initiation patients will be seen at an outpatient clinic. During this visit baseline examinations will be performed and NovoTTF-200A treatment will be initiated under medical supervision. The patients will also be instructed on the operation of the NovoTTF-200A and battery replacement. Once the patients are trained in operating the device they will be released to continue treatment at home. The patients will receive multiple 1 month courses of continuous NovoTTF-200A treatment.

NovoTTF-200A treatment will be stopped in the following cases:

1. Treatment will be stopped in the case of device related serious adverse events
2. Clinical and functional deterioration considered by the investigator to be prohibitive of continuing treatment.
3. Radiological progression
4. Re-operation, for the patients where the pathology is consistent with necrosis (pseudo-progression). NovoTTF-200A treatment will be interrupted for at least 2 weeks after reoperation or until wound healing).

As long as the patients are receiving treatment (NovoTTF-200A), all patients will be seen once every month at an outpatient clinic where they will undergo medical follow-up and routine laboratory exams. An MRI will be performed every second month following the baseline MRI.

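### The supplemental per-protocol set is selected on device use during follow-up with no fixed window or landmark, so its PFS6 can shift even if adherence has no effect

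*Combined protocol and SAP*

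**What the plan says.** Section 8 (Analysis Data Sets for Efficacy, repeated in the synopsis) puts the primary efficacy analysis on the ITT set, meaning everyone who has used the device at all. It adds a supplemental PP set, "defined as including only those participants meeting the minimum prescription for device use", with the criterion given as at least "18 hours daily over a four-week cycle".

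Other places word the adherence target differently. Footnote 10 of the schedule of assessments applies it as a monthly rate "of therapy over each 4-week cycle in subjects until progression". The synopsis gives a monthly rate of at least 75%, equated with 18 hours a day, as something encouraged or as a goal.

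The primary endpoint is disease status six months after treatment initiation, and no other time origin is given for PFS or OS. Section 3.1 ends device use at progression: "In the case of radiological progression, NOVOTTF-200A treatment will be stopped". It also ends use when clinical decline makes continuing prohibitive in the investigator's view.

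The PP set is carried into the Kaplan-Meier, log-rank and Cox analyses of Section 8.1: "Secondary analyses will be performed on both the ITT and PP data sets, as seems warranted".

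**The concern.** The PP definition does not say which cycle counts, whether one cycle or all must qualify, whether 18 hours is a daily floor or a mean, or how to classify a patient who stops mid-cycle. Membership is therefore decided by data that accrue during the period over which the outcome is measured.

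- If any one cycle is enough, patients who stay on treatment longer have more chances to enter PP.
- If every cycle must qualify, they have more chances to fall out.
- If Cycle 1 must be completed, patients who stop during it drop out of PP.
- Under any reading, a patient who is declining may use the device less, so low use can be an early sign of progression.

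A PP result is naturally taken as the outcome with adequate device use. Here it could show an apparent benefit or deficit that comes only from time on treatment. The trial is open-label and single-centre, and nothing stops the reading being settled after outcomes are known.

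**Working it through.** **The plan's own figures.** Section 8.1 gives precision for 34 subjects and nothing for the PP set. I took the exact (Clopper-Pearson) 90% interval for each count x out of 34 and summed the Binomial(34, p) probabilities over those x whose half-width is at most w. At p = 45% and w = 15% this gives 0.468, against the stated 0.47. All 18 cells agree within 0.02.

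**Inputs from the documents.** Cycles last 28 days. MRI is at the end of each even-numbered cycle (every 56 days), with an unscheduled scan on clinical progression. Device use stops at radiological progression.

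**Assumptions.** True PFS6 is 45% (a row of the plan's table). Six months is 182.6 days. Progression times are exponential. Each cycle meets the threshold with probability q, independently of other cycles and of progression. The documents give no share of patients meeting the threshold, so q runs from 0.5 to 0.9. Adherence has no effect on outcome, so any shift is selection alone.

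**Formulas.** The hazard is -ln(0.45)/182.6 = 0.004373 per day. The number n of completed cycles for a patient progressing at day t is:
- Setting A, progression stops use at once: n = floor(t/28).
- Setting B, progression is found only at the next scheduled MRI: n = 2 × ceil(t/56).

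The probability w(t) of being in PP is:
- any cycle: 1 - (1-q)^n
- every one of the first six: q^min(n,6), or 0 if n = 0
- Cycle 1 completed and met: q if n ≥ 1, otherwise 0

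PP PFS6 is the integral of w(t)f(t) over t > 182.6 divided by its integral over all t, where f is the exponential density. PFS6 is scored on the true progression time in both settings.

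**Results (unselected value 45%).**

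| Reading | q | Setting B | Setting A |
|---|---|---|---|
| Any cycle | 0.5 | 48.2% | 56.6% |
| Any cycle | 0.9 | 45.1% | 51.5% |
| Every one of first six | 0.8 | 31.9% | 33.2% |
| Every one of first six | 0.9 | 39.0% | 42.6% |
| Cycle 1 | any | 45.0% | 50.9% |

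The shifts are about 0 to +12 points (any cycle), -13 to -2 (every cycle) and 0 to +6 (Cycle 1). The last can be checked by hand: the chance of being progression-free at day 28 is exp(-0.004373 × 28) = 0.885, and 0.45/0.885 = 0.509.

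**Another base rate.** At a true PFS6 of 55% in setting A, Cycle 1 gives 60.3% (+5) and any cycle gives 60.9-65.4% (+6 to +10). Every one of six gives 52.3% (-3) at q = 0.9, falling to 10.6% (-44) at q = 0.5.

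**Clustering.** Let q vary between patients as a beta distribution with within-patient correlation 0.6 (assumed): a = q(1/0.6 - 1), b = (1-q)(1/0.6 - 1). The chance of meeting all k cycles is the product of (a+i)/(a+b+i) for i = 0 to k-1. At mean q of 0.8-0.9 in setting B, the every-cycle rule gives 43-44% and the any-cycle rule about 46%. In setting A the every-cycle rule gives 48.0-49.5%: the reduction disappears and the effect of having to complete Cycle 1 remains.

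**The case against.** The strongest reply is that this is a gap in the definition of a set on which nothing formal depends. PP is supplemental. The primary 90% interval is on ITT, neither the sample size nor the futility rule uses PP, and Section 8.1 treats secondary p-values only as a guide. All of that stands, and it limits the consequence.

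Three stronger readings are tempting, and the documents do not support them.

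- **That PP is biased by construction.** The sign and size depend on a reading the text leaves open. A Cycle 1 rule gives no shift if progression is found only at scheduled scans. The larger every-cycle shifts also rest on independence between cycles. With clustering and scan-only detection they fall to about 1 to 2 points.
- **That PP would hold only about half the patients.** One might infer this from the pilot in Section 1.2: "Patients received treatment on average about three quarters of the scheduled time". A mean equal to the 75% cut-off does not imply that half qualify. The same section reports a median of 20 hours a day in the phase III TTF arm, above the threshold. The size of PP cannot be predicted from the documents.
- **That adherent and non-adherent patients would differ dramatically.** Under the any-cycle rule at q = 0.5 in setting B, patients outside PP have a PFS6 of about 1%. They are only about 7% of patients (roughly 2 of 34), and no comparison of PP with non-PP patients is specified.

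**Conclusion.** The concern holds in limited form. PP membership rests on post-baseline device use with no fixed window or landmark, while outcome is counted from treatment start and use ends at progression or decline. PP PFS6 can therefore be distorted without any adherence effect, upward or downward according to the reading.

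The sizes calculated here are illustrations. They rest on exponential PFS, a 45% base rate, the chosen q values, and independence of cycles from each other and from progression. Reduced use in declining patients is not quantified; it would push the PP result upward under any reading.

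The point deserves correction because PP enters the survival analyses meant to inform further research, and a better definition is cheap. It casts no doubt on the primary ITT estimate.

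**What to change.** In Section 8:

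1. Define PP by mean daily use in Cycle 1, taken from the device log, against the plan's existing 18-hour threshold.
2. Analyse PP PFS and OS from a day-28 landmark among patients alive and progression-free then. The landmark deals with the up to +6 points that arise when patients progressing in Cycle 1 drop out of PP.
3. Reconcile the *a cycle*, *each cycle* and monthly-rate wordings across Section 8, the schedule footnote and the synopsis. This concerns the analysis definition and takes no position on the device-use target itself.
4. Label PP results descriptive, because low use even in Cycle 1 may reflect early decline.

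Any time-dependent adherence covariate in the Cox model should be exploratory only. It is directly exposed to reverse causation, and there are at most 36 patients.

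The cost is a few sentences. Section 6.2.2 already provides for periodic log downloads. Patients with events before day 28 leave the PP analysis but stay in ITT. The PP estimate becomes conditional on reaching day 28, so it should not be set directly against the ITT figure: in the illustration above, conditioning alone takes 45% to 51%. The fair comparison is all patients from the same landmark.
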